8.8.5 Dose limiting toxicity (DLT)

For the purposes of this trial, a dose-limiting toxicity will be classed as an AE grade 3 or higher of the following

- anaemia
- haemolytic anaemia
- liver function impairment (increased alanine aminotransferase; increased alkaline phosphatase or increased blood bilirubin)
- kidney function impairment (increased creatinine or chronic kidney disease)

as defined by the Common Terminology Criteria for Adverse Events (CTCAE), Version 5.0, Published: November 27, 2017. See appendix 4 for grading details.

Participants will be monitored for occurrence of DLTs during the Stage 1 trial visits, which are known to be rare at the recognised CBZ dose for treatment of the licensed indications (epilepsy, the paroxysmal pain of trigeminal neuralgia and the prophylaxis of manic-depressive psychosis in patients unresponsive to lithium therapy).

If more than one participant experiences a DLT during the stage 1 dose titration and tolerability, the dose-regimen will be reviewed by the TMG, input from the IDMC will be sought and appropriate modifications made. These events are unlikely, as the trial does not plan to exceed the recognised dose for treatment of licensed indications for CBZ.

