5.2 Stage 1 (UK only) – Dose titration and tolerability & treatment

Stage 1 is a dose titration of carbamazepine in 5mg/kg increments to a preselected maximum dose of 20mg/kg, with review of safety and tolerability in a population of 11 participants from two UK trial sites over a 12 month period (See Table 6). A safety review will be conducted, once the 11th patient has reached the 6 month time point. For a detailed description of the Stage 1 dose titration, see section 8.8. Once a suitable dose is agreed, Stage 1 participants will continue CBZ treatment at this agreed dose until they reach 24 months treatment (See Table 7). There will also be an opportunity to continue CBZ treatment for an additional 12 months for participants who wish to do so. This optional CBZ treatment will be a subject to an additional informed consent at visit 2.5. Their 12/24 month data will be included in the final analysis following Stage 2, subject to IDMC consultation.

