8.7.5 Laboratory safety assessments

A blood sample will be taken for full blood count (approximately 1ml), and for kidney function and liver function tests (maximum 1ml) at times specified in the schedule of events (Tables 5, 6, 7, 8 & 9). These tests are comprised of:

- Full blood count (haemoglobin, platelets & white cells neutrophils & lymphocytes)
- Kidney function test: creatinine, serum electrolytes, eGFR
- Liver Function test: total bilirubin, ALP, ALT or AST (site dependent)

A urine sample will also be taken to measure proteinuria using a dipstick at times specified in the schedule of events (Tables 5, 6, 7, 8 & 9).

Samples will be processed at the trial site local or associated laboratories, following standard local laboratory procedures.

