If the participant is reporting any side effects /adverse events of significant concern to the clinician which are suspected to be related to the IMP as listed within the approved CBZ (Tegretol[®]) SmPC (PI^b for Australia) and/or accompanying Patient Information Leaflet, they will be asked to attend the trial site for laboratory safety blood assessments and further review. The results of the laboratory safety blood assessments, reported side effects/adverse events and clinical examination of the participant will be used to inform any changes to the participant's current dose.

If the participant is reporting any severe side effects as detailed in the CBZ (Tegretol[®]) SmPC (PI^b for Australia) and/or Patient Information Leaflet which prevent the participant from adhering to the trial protocol or in the opinion of the investigator deem the participant not suitable to continue participation in the trial then CBZ should be permanently discontinued and the patient withdrawn from the trial. The patient will be contacted again within 7 days to ensure the reasons for withdrawal have been resolved to the satisfaction of the investigator. If the participant experiences any severe side effects beyond the dose titration and tolerability stage, the same approach will apply.

Participants who do not tolerate increased dosing will be kept on a lower dose or the dose will be reduced. The inclusion of such patients in the final efficacy analysis will be discussed and evaluated case by case by the TMG with input from the IDMC if required (see section 8.8.4 – Missed doses).

If an adverse event is deemed to be serious, then a Serious Adverse Event form will also need to be completed (see protocol section 10.2 – Recording and reporting of AEs and SAEs) and sent to NCTU (UK only).

8.8.2 Dose evaluation safety visits – Week 2

To ensure patient safety during the escalation of dose from 5mg/kg to 20mg/kg participants and their parent(s)/legal guardian(s) will attend a site trial visit at week 2 (+/- 1 day). Blood samples will be taken to conduct the laboratory safety assessments described in section 8.7.5. Medication counselling will be provided if required. Once the outcomes of the laboratory safety assessments have been received at the trial site, a follow-up phone call will be made to the participant and their parent(s)/legal guardian(s) to discuss any requirement to alter their dose regimen. Additional assessments including

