adverse event reporting and recording of concomitant medication will also be conducted during this visit as indicated in Table 6.

8.8.3 Dose evaluation safety visits – Months 3, 6, 9 & 12

Participants will be further assessed at clinic visits scheduled at 3, 6, 9 and 12 months post dose titration commencing. Assessments will include physical examination, Tanner stage, growth measurements, X-rays (left wrist for bone age and long leg standing AP), laboratory safety assessments, pregnancy testing (potentially child bearing females only), EQ-5D-Y questionnaire, PEDSQL questionnaires, AE recording, drug prescription & medication counselling, recording of concomitant medications and biomarker blood sampling (UK participants only) as detailed in the schedule of events Table 6.

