8.10 Premature stopping of the trial

There are no formal stopping guidelines for the trial. However, if more than one participant experiences a DLT during the stage 1 dose titration and tolerability, the dose-regimen will be reviewed by the TMG, approval from the IDMC will be sought and appropriate modifications made. These events are unlikely, as the trial does not plan to exceed the recognised dose for treatment of licensed indications for CBZ.

8.11 Storage and Analysis of Biomarker Samples (UK sites only).

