11.2.3 Interim Analyses and Criteria for the Premature Termination of the Trial

An interim safety analysis will be conducted after the first six patients in Stage 1 have reached their maximum tolerated dose or 20mg/kg. Data presented to the IDMC for review will include the number and reason for any DLTs, all laboratory safety assessments, pain scores and all adverse events. The IDMC will recommend or oppose continuation of the trial to the TSC.

A further, similar, safety analysis will be presented to the IDMC on completion of Stage 1. There are no formal stopping rules.

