1.2 Stage 1 summary

The primary objective of Stage 1 was to assess the safety and tolerability of CBZ in the treatment of children with MCDS who are ambulant but have not yet reached skeletal maturity (open epiphyses) and to determine an appropriate dose of CBZ to inform the treatment of children in Stage 2.

A cohort of eleven patients were evaluated through a review of safety and tolerability. Data presented to the DMC included the number and reason for any DLTs, laboratory safety assessments, abnormal physical examinations, pain scores and adverse events. Initially, the Stage 1 safety review [report dated 9/8/2021] was presented to the IDMC when six patients in Stage 1 reached their maximum tolerated dose or 20mg/kg. A subsequent report was presented to the DMC [25/10/2021] once the last patient on CBZ in Stage 1 reached the 6-month time point.

Following these reviews, the IDMC recommended continuation of the trial according to the current version of the protocol (Version 6.0 dated 30 June 2021) with no changes and agreed that the IMP dose regimen to be implemented in Stage 2 of the study should be 20 mg/kg.

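### AST is a permitted liver test but not a DLT term, so at an AST-only site an isolated grade 3+ AST rise would fall outside the Stage 1 DLT count and review trigger

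*Protocol*

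**What the plan says.** The liver panel in Protocol 8.7.5 is "Liver Function test: total bilirubin, ALP, ALT or AST (site dependent"), so a site may run one transaminase and not the other.

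Protocol 8.8.5 defines a DLT as an adverse event of grade 3 or higher from a fixed list. Its liver item is "liver function impairment (increased alanine aminotransferase; increased alkaline phosphatase or increased blood bilirubin"). The list has no catch-all for other hepatic toxicity. Protocol Appendix 4 and SAP section 7 each give seven grading rows: anaemia, haemolysis, ALT, ALP, bilirubin, creatinine and chronic kidney disease. Neither has a row for AST.

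The site-dependent panel is the one used while DLTs are being counted. At the week 2 visit (8.8.2), "Blood samples will be taken to conduct the laboratory safety assessments described in section 8.7.5". After that, "Participants will be further assessed at clinic visits scheduled at 3, 6, 9 and 12 months post dose titration commencing" (8.8.3), and Table 6 schedules the laboratory safety assessments at each of those visits. Stage 1 takes place "in a population of 11 participants from two UK trial sites over a 12 month period" (5.2).

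The DLT label is used in three places:

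- **Review trigger (8.8.5, 8.10):** "if more than one participant experiences a DLT during the stage 1 dose titration and tolerability, the dose-regimen will be reviewed by the TMG", with the IDMC involved.
- **Withdrawal (8.9):** more than one DLT in a participant is given as an example of unacceptable toxicity.
- **IDMC report (11.2.3):** the package includes "the number and reason for any DLTs, all laboratory safety assessments, pain scores and all adverse events". SAP 1.2 confirms what was sent: "Data presented to the DMC included the number and reason for any DLTs, laboratory safety assessments", together with physical examinations, pain scores and adverse events.

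**The concern.** One permitted laboratory panel cannot detect one of the trial's own DLTs. A child at an AST-only site could have a grade 3 or higher transaminase rise that the rule does not recognise, while the same liver injury at an ALT site could be recognised through ALT.

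At stake are the accuracy of the Stage 1 DLT count and one extra review of the dose regimen. Safety and tolerability is a Stage 1 primary objective, and the Stage 1 reviews led the IDMC to agree 20 mg/kg for Stage 2 (SAP 1.2). A DLT count quoted from Stage 1 should therefore mean the same thing for every child in it.

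**Working it through.** The documents give no figure on this point, so there is none to reproduce. The check compares the texts and then works out when the omission would change a result.

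**Step 1: what each panel can detect**

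| Liver test | Allowed by 8.7.5 | DLT term in 8.8.5 | Row in Appendix 4 and SAP section 7 |
|---|---|---|---|
| Bilirubin | all sites | yes | yes |
| ALP | all sites | yes | yes |
| ALT | site option | yes | yes |
| AST | site option | no | no |

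The ALT row in Appendix 4 is specific to that enzyme, and no text says AST may stand in for it. Bilirubin and ALP are only a partial backstop, because an isolated AST rise meets neither. A footnote to Appendix 4 also restricts the ALP criterion to ALP of liver origin.

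**Step 2: effect on the count and the trigger**

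Inputs: 11 Stage 1 participants (5.2); the trigger is two or more participants with a DLT (8.8.5, 8.10). Let

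- d = Stage 1 participants with a DLT as listed;
- m = participants at an AST-only site with a grade 3 or higher AST rise and no listed DLT.

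The count as written is d. The count with AST included is d + m. The shortfall is (d + m) − d = m. The trigger as written is d ≥ 2; with AST included it is d + m ≥ 2.

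| | m = 0 | m = 1 | m ≥ 2 |
|---|---|---|---|
| d = 0 | no review either way | no review either way | **review missed** |
| d = 1 | no review either way | **review missed** | **review missed** |
| d ≥ 2 | review either way | review either way | review either way |

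The documents give neither d nor m, nor which transaminase each UK site ran. If both sites ran ALT, m = 0 and nothing changes. Otherwise m cannot exceed the number of children at AST-only sites, which lies somewhere from 1 to 11. No event rate is assumed.

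**Step 3: size of a retrospective check**

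Table 6 schedules five laboratory draws per child after the start of treatment: week 2 and months 3, 6, 9 and 12. That gives 11 × 5 = 55 panels at most, fewer if a child withdrew or a draw was missed, plus any ad hoc samples. Three of the five fall at or before month 6, the time point for the dose-setting review: 11 × 3 = 33.

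**The case against.** The strongest reply is that neither patient protection nor oversight depended on the DLT label.

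- After the week 2 bloods, a call to the family considers any dose change, with no DLT condition (8.8.2).
- Side effects of significant concern bring the child in for safety bloods that inform the dose, and severe ones can lead to permanent discontinuation (8.8.1). Withdrawal under 8.9 is open to the investigator for any reason.
- Both scheduled dose-setting reviews (8.8.6) went ahead whatever the DLT count, with laboratory data and adverse events in the package (11.2.3, SAP 1.2).
- The trigger leads to a review and not to a stop; there are no formal stopping rules (8.10, 11.2.3).
- SAP section 5 already plans to report out-of-range laboratory results by participant, list every adverse event with its severity, and give the number of patients with grade 3 to 5 events. It plans no DLT table.

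All of this stands, and it is why the point is minor. It does not remove the mismatch. Laboratory values elsewhere in a report neither correct a formal count nor set off a formal trigger.

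A second reply also stands: the gap may be empty. The site-dependent wording serves both stages and all seven sites in Table 3, while the review trigger applies only to Stage 1 at two UK sites.

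**Conclusion.** The mismatch is clear on the text, and its severity is minor. At an AST-only site, an isolated AST rise of grade 3 or higher would not count toward the Stage 1 trigger, the withdrawal example in 8.9 or the DLT number given to the IDMC. The count would be low by exactly m. The trigger would be missed only if d = 0 with m of 2 or more, or d = 1 with m of 1 or more.

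This is conditional on a UK Stage 1 site having run AST without ALT, which the documents neither state nor rule out.

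A reader might infer that liver toxicity went unnoticed in Stage 1, or that 20 mg/kg was agreed without sight of it. The documents do not support either inference. They report no AST rise and no AST-only UK site, and the IDMC had laboratory data and adverse events as well as the DLT count. The likely effect is confined to the formal count and the formal trigger.

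**What to change.** **Definition.** The liver item should read increased ALT or AST, with an AST row in the grading tables; alternatively, ALT should be required at every site. That is a few words in 8.8.5, Appendix 4 and the SAP appendix. It belongs in any reuse of the definition. It should not be presented as the rule under which the IDMC reviewed the data in 2021.

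**Stage 1 data.** Stage 1 is complete, so the useful step now is a single check:

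1. Record which transaminase each of the two UK sites ran.
2. If both ran ALT throughout, say so in one sentence and close the point.
3. If either ran AST only, check its share of the at most 55 scheduled panels after the start of treatment, plus any ad hoc ones, for AST of grade 3 or higher. Take the grading from CTCAE v5.0 itself, since the appendices do not reproduce the AST criteria.
4. In that case, report the Stage 1 DLT count under the definition in force with a stated limitation, and give any AST-inclusive count separately, labelled post hoc.

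The cost is small, because the SAP already calls for participant-level listings of out-of-range results. The one drawback is that the AST-inclusive count may exceed the number the IDMC saw; the separate post hoc label deals with that.

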8.8.6 Dose finding review

An interim safety analysis will be conducted when at least six patients reach their MTD, which will allow modification of the regimen if required. The review will be led by the CI, Sponsor will be consulted and agreement from the trial IDMC will be sought. The review will be based on laboratory

safety assessments, adverse events and pain questionnaires. Treatment of the remaining stage 1 participants will not be delayed while this review is ongoing.

Once all 11 participants have reached 6 months (or those who are still continuing / not withdrawn), a safety review will be conducted to formally agree the IMP dose regimen to be implemented in Stage 2 of the study. Data to be reviewed includes laboratory safety assessments, adverse events, and pain questionnaires. The review will be led by the CI, Sponsor will be consulted and agreement from the trial IDMC will be sought.

Handling and review of data for both safety reviews will be performed in accordance with the trial Data Management Plan and Statistical Analysis Plan.

Participants who do not tolerate dosing will be kept on a lower dosing or dosing reduced. The inclusion of such patients in the final efficacy analysis will be discussed and evaluated case by case by the TMG with input from the IDMC if required.

Table 10 Timing and Frequency of reviews

Review	Time	Outcomes	IDMC agreement required
Interim safety analysis	First 6 patients reach MTD or 20mg/Kg	Primary outcome (SAFETY): Laboratory safety assessments, adverse events, pain scores and physical examinations collected post IMP administration.	Yes
Safety Review	11 th patient reaches the 6 month time point (or those who are still continuing / not withdrawn),	Primary outcome (DOSE) : Outcome of dose-titration safety review at 6 post IMP treatment initiation.	Yes, required to agree dose for Stage 2
Completion of Stage 1 safety analysis and Pain analysis	12 months from Baseline (when last patient recruited has reached 12 month time point) A further safety analysis will be presented to the IDMC on completion of Stage 1	 Primary outcome (SAFETY): Laboratory safety assessments, adverse events, pain scores and physical examinations collected post IMP administration. Secondary outcome (PAIN): Alteration from baseline in pain perception over 12 months as measured by: PEDSQL Pain Coping Inventory PEDSQL Pain Questionnaire 	No, to be presented at next IDMC meeting following analysis

8.8.7 Continuation of treatment with CBZ for Stage 1 participants

Assuming Stage 1 participants have achieved their MTD and no significant safety concerns arise from the dose titration 6 month safety review, participants from Stage 1 will continue treatment with CBZ. They will receive the dose approved by the trial IDMC until they have received 24 months of IMP treatment (post initiation of IMP treatment) to allow their data to be included in the Stage 2 final analysis. If a participant has not reached the dose approved by the trial IDMC, they will continue on the maximum dose they were able to tolerate until they have received 24 months of IMP. Stage 1 participants will continue to attend trial visits every three months as indicated in the schedule of events –treatment (Table 7) and the participant visit schedule (Table 4). Eligible Stage 1 participants in the UK, who commenced treatment before 2nd March 2021, will have the option to continue treatment with CBZ for an additional 12 months after they have completed 24 months of IMP treatment. All trial visits must be completed by 31st January 2024.

Assuming the dose regimen is sufficiently similar in stage 1 and 2, stage 1 patients will be included in the analysis at the end of the trial, using the primary endpoint measured at the end of the dose titration phase for stage 1 and at the end of 12 months of treatment for stage 2. If the dose regimen changes between stage 1 and stage 2, we will consult with the IDMC as to whether stage 1 and stage 2 patients should be combined in the final analysis.

8.9 Withdrawal Criteria

Participants have the right to withdraw from the trial at any time without having to give a reason. Investigator sites should try to ascertain the reason for withdrawal and document this reason on the eCRF within the trial MACRO database and in the participant's medical notes.

The Investigator may discontinue a participant from the trial at any time if the Investigator considers it necessary for any reason including:

- Pregnancy
- Participant withdrawal of consent/assent
- Investigator's discretion that it is in the best interest of the participant to withdraw
- An adverse event that requires discontinuation of the trial medication or renders the participant unable to continue in the trial
- If a participant experiences unacceptable toxicity (more than one DLT)

If a trial participant withdraws from the trial all data collected to the point of withdrawal will be retained. Consent/assent will have been sought to allow this.

It should be noted that participants may also be given the option to withdraw from treatment only, but continue with follow-up as per the protocol schedule. This will be explicitly documented in the participants medical notes and within the eCRF.

8.10 Premature stopping of the trial

There are no formal stopping guidelines for the trial. However, if more than one participant experiences a DLT during the stage 1 dose titration and tolerability, the dose-regimen will be reviewed by the TMG, approval from the IDMC will be sought and appropriate modifications made. These events are unlikely, as the trial does not plan to exceed the recognised dose for treatment of licensed indications for CBZ.

8.11 Storage and Analysis of Biomarker Samples (UK sites only).

8.11.1 Collection

A maximum of 2ml blood will be taken for exploratory biomarker analysis at times specified in the schedule of events (Tables 5, 6, 7, 8 & 9). Additionally, a maximum of 2ml of blood will also be taken for the measurement of Bone markers (osteocalcine and CTX), if available at site.

Serum will be prepared at both UK clinical centres and will be collected in appropriate tubes to be supplied by the relevant clinical centres.

Serum samples will be shipped to the Newcastle MRC Centre Biobank for Rare and Neuromuscular Diseases based at the Institute of Genetic of Medicine, Newcastle University, on the day of collection if possible; otherwise, they will be stored locally (in a -80°C freezer) and shipped to the Newcastle MRC Biobank as soon as convenient and in accordance with the Trial Laboratory Manual.

For serum sample volumes, aliquoting and processing requirements please consult the trial Laboratory Manual.

8.11.2 Analysis

Proteomics and microRNAseq analysis of serum samples will take place in specialist facilities at Sciomics, Heidelberg and at the Skeletal Research Group, Institute for Genetic Medicine (IGM), Newcastle University respectively.

The Newcastle MRC Centre Biobank for Rare and Neuromuscular Diseases biobank manager or appointed delegate (technician) will be responsible for the appropriate shipping of samples to Sciomics. Serum samples for proteomics analysis will be shipped to Sciomics on dry ice in appropriate batches. Screening will be undertaken using the scioDiscover platform (semi-targeted affinity proteomics platform) to identify biomarker candidates during the course of the trial. Following an initial discovery phase (using cell and mouse model samples), serum samples will be collected from UK patients undergoing CBZ treatment in both Stage 1 and Stage 2. Patient samples will be profiled on custom microarrays containing selected proteins identified from the mouse and cell line analysis.

Serum samples destined for microRNAseq analysis at IGM will be collected from the biobank in person by an approved researcher. The Newcastle MRC Centre Biobank for Rare and Neuromuscular Diseases will also provide control samples for the microRNAseq analysis.

MicroRNA analysis (IGM Newcastle) will be performed on the HTG EdgeSeq microRNA Whole Transcriptome Assay system which measures the expression of 2,083 individual human microRNA transcripts in serum with minimal processing time by high-throughput sequencing. The novel technology employed avoids much of the bias in data generation to which other small RNA-seq methods are prone. Simply following sequencing DESeq2 is used for library size normalisation and differential expression analysis.

